6.4 Description of the intervention

The patients of the experimental group will receive the food supplement Lit-control®pH Down to help maintain the urinary pH at the levels considered as preventive for stent calcification (pH <6.2), with the indicated guideline of 3 capsules per day. On the contrary, the control group will receive a placebo product with similar organoleptic characteristics with the same dosage. Both groups will use the Lit-Control® pH Meter device for urinary pH self-monitoring as well as receiving the same indications for stent care.

The intervention group will be assigned to each patient according to the assigned code in order of inclusion to the study and that will serve for the randomization of the patients.

6.5 Randomization

Patients will be randomized into two groups according to whether they receive the dietary supplement Lit-control®pH Down or placebo. The random assignment of patients will be implicit in the code that will be assigned consecutively in each center. The code lists for the centers will be previously prepared through an ad-hoc program. The ratio between placebo and Lit-Control® pH Down will be 1: 1. Being a competitive inclusion, the randomization numbers will be distributed in blocks of 5 for each center, with an average of three deliveries per center.

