6. STUDY DESIGN

6.1 Type of study

Clinical trial with medical device (Lit-control®pH Meter device). Multicenter, prospective, randomized, double-blind, placebo-controlled study in adult patients who come to the urology / nephrology clinic who have recently had a double J stent or have their placement programmed and who are able to take charge of the urinary pH control at home.

They will be randomized into two groups (experimental group (Lit-control®pH Meter + food supplement Lit-control®pH Down) and control group (Lit-control®pH Meter + Placebo)). The ratio will be 1: 1 between the experimental group and the control.

In accordance with the current Royal Decree 1090/2015, of December 4, which regulates clinical trials with medicines, the Research Ethics Committees with medicines and the Spanish Registry of Clinical Studies, 18 a new type is contemplated a "low level of intervention" test in which less rigorous standards are adopted in aspects such as monitoring, the content of the master file or traceability, without impairing the safety of the individuals who participate in them. This concept was introduced by Regulation (EU) No. 536/2014 of the European Parliament and of the Council of April 16, 2014,¹⁹ which quotes verbatim:

"The risk to the safety of the test subjects comes mainly from two sources, the investigational drug and the intervention, but many clinical trials pose an additional risk to the safety of the subjects that is minimal compared to that of clinical practice. habitual. This is so, specifically, when the investigational medicinal product already has marketing authorization, which means that its quality, safety and efficacy were already evaluated during the authorization procedure or, if that medication is not used in accordance with the conditions of the marketing authorization, when its use is based on evidence and is supported by documented scientific data on the safety and efficacy of that medicine, and the intervention only involves a very limited additional risk for the test subject, compared with that of the practice usual clinic. "

In the same regulation, a "low-level intervention clinical trial" is defined:

- a) investigational drugs, excluding placebos, are authorized;
- b) according to the protocol of the clinical trial:
 - i. the investigational drugs are used in accordance with the terms of the marketing authorization, or

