6.8 Predetermination of the sample size

For the calculation of the sample size, the non-parametric Mann-Whitney U test was used for independent groups in order to observe, on a 4-point stent calcification scale (0-3), a difference equivalent to a size Effect of 0.6.

Thus, considering a statistical power of 80% and a non-normal distribution, a sample size of 94 patients is obtained. In anticipation of a 10% loss, the sample is extended to 105 patients.

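### Does distributing randomisation numbers in fives per centre conflict with the 1:1 allocation ratio?

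*Protocol*

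**What the plan says.** Protocol section 6.1 sets the ratio: "The ratio will be 1: 1 between the experimental group and the control". Section 6.5 repeats it ("The ratio between placebo and Lit-Control® pH Down will be 1: 1") and then describes the mechanics in three steps.

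- The lists come first: "The code lists for the centers will be previously prepared through an ad-hoc program".
- Patients receive codes in sequence: "The random assignment of patients will be implicit in the code that will be assigned consecutively in each center".
- Because centres recruit competitively, "the randomization numbers will be distributed in blocks of 5 for each center, with an average of three deliveries per center".

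Section 6.8 gives the total: "the sample is extended to 105 patients", from 94 evaluable patients and a 10% loss. No other block size appears in the protocol. Section 8.2 names two-sample tests (Student's t, Mann-Whitney, chi-square, Fisher) and no term for centre.

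**The concern.** In a section on randomisation, a reader expects the word block to mean the permuted block. With two arms at 1:1, a permuted block must be of even size. A block of five can be at best 3:2 or 2:3, and the protocol gives no rule for pairing the two kinds. Someone writing the list program from this sentence alone could set the block size to five.

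The possible costs are looser balance within centres, some drift from 1:1 overall, and a small loss of power. If five is instead a shipping quantity, the remaining complaint is that the true block size is not stated and that the word is used loosely.

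**Working it through.** **Inputs.** Two arms at 1:1 (sections 6.1 and 6.5); groups of five numbers and an average of three deliveries per centre (6.5); a Mann-Whitney test, effect size 0.6, power 80%, 94 evaluable and 105 in total after 10% loss (6.8). Assumptions: two-sided alpha of 0.05, because section 6.8 states none; equal centres; and, where five is taken as the block, 3:2 or 2:3 chosen at random for each block.

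**The plan's own figure.** Noncentral-t power with d = 0.6 and group sizes scaled by the Mann-Whitney efficiency 3/π gives 47 per arm, so N = 94, with power 80.3%. Then 94/(1 − 0.10) = 104.4, rounded up to 105. Both stated figures reproduce, which supports the assumed alpha.

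**Layout implied by section 6.5.** 105/5 = 21 groups of five. Three deliveries are 15 numbers per centre, and 105/15 = 7 centres.

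**Reading 1: five is a delivery batch.** Lists are made per centre and codes are used in order, so cutting a list into fives does not alter the sequence of assignments. With an underlying block of 4, for example, a centre of 15 uses three full blocks (6:6) and three places of the next, which always gives 8:7. Balance and power are untouched.

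**Reading 2: five is the permuted block.**

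*Overall balance.* Let K be the number of blocks favouring one arm, K ~ Binomial(21, 0.5). The arm difference is |2K − 21|.

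- Difference at most 3 (K from 9 to 12): probability 0.617.
- Difference at most 9 (K from 6 to 15): probability 0.973.
- All 21 blocks in one direction (63:42): 2 × 0.5^21, about 1 in 1,050,000.
- With 3:2 and 2:3 alternating, the split is 53:52, the closest that an odd total allows under any scheme.

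*Power.* The 94 evaluable patients are divided in each ratio, with the same approximation. The noncentrality is 0.6 × √[(3/π) × n1 × n2/(n1 + n2)].

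| Split of 105 | n1, n2 among 94 | Power |
|---|---|---|
| Balanced | 47.0, 47.0 | 80.3% |
| 54:51 | 48.3, 45.7 | 80.2% |
| 57:48 | 51.0, 43.0 | 80.0% |
| 63:42 | 56.4, 37.6 | 78.6% |

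*Balance within centres.* A centre of three blocks ends 9:6 when all three lean the same way: 2/8 = 0.25. Over seven centres, 7 × 0.25 = 1.75 are expected, and the chance of at least one is 1 − 0.75^7 = 0.867. For comparison, a fixed block of 4 never gives 9:6 at 15 patients. A fixed block of 6 does so when the first three places of the third block go to one arm: 2/20 = 10%. Even blocks are therefore tighter, but the difference is one patient moved from 8:7 to 9:6.

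**The case for a change.** The strongest case for a change is that the only block figure in the protocol, read literally, cannot be 1:1, so two competent people could build different lists from the same sentence. An odd block loosens balance within centres and brings no benefit, and the repair would be one sentence with no extra patients. This is not a request to print a block size that is better kept from sites; it is a complaint about the one number that is printed.

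Part of this stands. The sentence is loosely worded, a block of five has no equal split, and the text never says outright that five is a shipment.

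The rest does not carry through. The sentence follows one that already says how the lists are made. It speaks of distribution and deliveries, and its stated reason is competitive recruitment. That reason explains sending numbers in instalments to centres of unknown final size; it does not explain a permuted-block size. If five is a batch, all that remains is an unstated block size, which may properly sit in a restricted randomisation document. If five is the block, the looser balance within centres has no shown consequence: the comparisons in section 8.2 do not use centre, treatment is masked with coded boxes (section 10.2), and allocation remains random.

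**Conclusion.** No change follows. The wording is ambiguous, but neither reading leads to an unsound trial. As a delivery batch, the more natural reading, five costs nothing. As a permuted block, it is compatible with the 1:1 ratio as stated, which applies between arms and not to each block or centre. It introduces no bias and lowers power by about 0.3 percentage points or less at splits up to 57:48. The largest loss, 80.3% to 78.6% or 1.7 points, needs all 21 blocks to go the same way.

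The power figures rest on a two-sided 5% level and the rank-test approximation that reproduces the plan's 94. The centre figures rest on seven equal centres and a random choice between 3:2 and 2:3. Which reading the sponsor intended cannot be settled from the protocol, but the conclusion does not depend on it. Calling the five a delivery batch would be an optional editorial improvement.

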6.6 Concomitant treatments

The existence of concomitant treatments will be recorded. Only those treatments likely to influence the results of the trial will be grounds for withdrawal from the study (see section 6.2.4).

6.7 Compliance with the intervention

Compliance with the indicated intervention will be verified with the data recorded in the Patient's Home Journal, with direct questions in the control visits and the empty blisters returned by the patients in the Vf.

6.8 Predetermination of the sample size

For the calculation of the sample size, the non-parametric Mann-Whitney U test was used for independent groups in order to observe, on a 4-point stent calcification scale (0-3), a difference equivalent to a size Effect of 0.6.

Thus, considering a statistical power of 80% and a non-normal distribution, a sample size of 94 patients is obtained. In anticipation of a 10% loss, the sample is extended to 105 patients.

7 VARIABLES AND MEASURING INSTRUMENTS

7.1 Main valuation variables

- Score on the scale of incrustation (main variable of effectiveness):
 - or 0 (Without inlay).
 - or 1 (Sporadic calcifications less than 1-2 mm²).
 - or 2 (Calcifications of wide areas greater than 1-2 mm²).
 - or 3 (Complete block).
- Urinary pH level and control of it below 6.2 (urine 2h fasting and home self-control with Lit-control®pH Meter).
- Reason for stent placement (approximately 90% is expected to be urolithiasis).
- Obstruction risk factor²³.
- Stent analysis / observation (presence of biofilm, degree of incrustation).
- Double J stent study:
 - o Scanning electron microscopy + micro-analysis by dispersive energy of RX: type and size of the crystals formed.
 - or ICP-AES spectroscopy (degree of global calcification of each end: Ca, Mg and P).
- Presence (Yes / No) and Degree of calcification (I-V) (Annex 7) ²⁴.

7.2 Secondary valuation variables

- Sociodemographic and anthropometric variables (sex, age, weight, height, BMI, marital status, work situation, toxic habits).
- Family history of obstructive uropathies.
- Personal clinical history of interest (previous nephritic colic, kidney transplant, acute pathology of interest, chronic pathology (HBP, Chronic Kidney Disease, Diabetes and others).

- Anatomical alterations in the urinary system.
- Previous incidence of obstructive uropathy (urolithiasis, stenosis and ureteral injuries, retroperitoneal fibrosis).
- Previous need for stent (indwelling stent reason, date of stent placement and removal, type of stent and symptoms (if any) associated with it)
- Date of placement and removal of the double J stent (current) and Total time with double J stent until its withdrawal (days).
- Total pH control time (days).
- Urine analysis of 2 hours in basal fasting (volume of urine, pH, creatinine, uric acid).
- Urine culture (infection: yes / no).
- Complications observed due to placement or permanence of the stent and symptoms associated with indwelling stent.
- Image of the stent (scanner or X-ray).
- Adherence to treatment / recommendations of the doctor.
- Adverse events attributable to the treatment or study recommendations.
- Data on stent removal (date, complications, type of procedure and duration of extraction).
- Satisfaction of the researcher with preventive therapy.
- Patient satisfaction with preventive therapy.
- Pharmacoconomic data (direct costs): stent placement intervention, consultation visits, emergency visits, hospitalizations, medication administered, intervention (cost and type) for stent removal and total direct cost of the patient during the study (estimated at from the data provided by the center).

7.3 Tools

- pH scale and cut points.
- Lit-Control® pH Meter device for measuring urinary pH (home self-monitoring).
- Scale of incrustation / blocking of the stent (0 / Without inlay - 3 / Complete block).
- Blockage risk factor (Clifford et al, 2000) 23 (in order to better characterize the sample studied) (See Annex 2).

7.4 End points

- Profile / Characteristics of the patient to whom a double J stent is placed.
- Comparison between groups of the results of the stent study (type and size of the crystals formed and degree of global calcification of each end).
- Success rate in pH control below 6.2 during the study.

- Percentage of stent extractions in the first attempt.
- Rate of complications in the extraction of the stent.
- Rate of adverse events attributable to treatment.
- Percentage of patients compliant (adherence > 80%) of the study interventions at 8 weeks (final visit).
- Degree of satisfaction of the researcher with the results of pH control.
- Degree of patient satisfaction with the use of the products under study.
- Cost-effectiveness of the intervention object of study according to the direct costs observed.

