Lit-control® pH Down is a dietary supplement with an acidifying effect on urine, which helps to prevent complications arising from the alkalinization of urine. It contains L-methionine, phytin (calcium-magnesium phytate salt), zinc and vitamin A. The two active components in acidification of pH_v are L-methionine and fintine, while zinc and vitamin A increase the action of the phytin. Specifically, zinc favors the affinity of its affinity for calcium phosphate and vitamin A prevents its degradation by alkaline phosphatase.

L-methionine is an essential amino acid that plays an important role in metabolic processes. It is normally acquired through food and absorbed in the small intestine to be metabolized in the liver via cysteine to sulphate and protons (ANNEX 8). Consequently, its administration produces a significant reduction of urinary pH.

According to the European Association of Urology (UAE), urinary acidification with L-methionine up to pH 5.8 - 6.2 is recommended as a therapeutic measure for calcifications of struvite, calcium phosphate and ammonium urate at doses of 600- 1500 mg / day¹³. This recommendation is based on the results observed in Jarrar et al 1996¹⁴, where an acidification of the pH of the urine of the patients was observed from 7.5 to 5.5 after the administration of 1500-3000 mg / day (3-6 capsules). of 500mg / day). Also in the study of Hesse 1999 a significant reduction in urinary pH was observed up to pH = 6.0 after the administration of a single dose of 1500 mg of L-methionine, maintaining this effect for 24h¹⁵. In addition, a significant reduction was observed versus the control group in terms of the relative supersaturation for estuvite and

brushite in the urine of 24h15. In another more recent study, Siener et al. studied the circadian course of urinary pH after the administration of 1500 mg of L-methionine. They observed a strong decrease in urinary pH up to 2h after the administration of the amino acid that remained at significantly low levels for 8h, resulting in a pH level for 24h between 5.98 and 6.3216. Therefore, in order to guarantee therapeutic doses of L-Methionine (1500mg / day), the Lit-control®pH Down regimen to follow would be equivalent to 3 capsules per day (500 mg / capsule).

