6.2.1 Inclusion criteria

- Age ≥18 years.
- Patients who have recently had a double J stent (time less than a week) or who have scheduled their placement and are recommended to control the pH to avoid scaling / calcification.
- Patients who agree to participate in the study and provide their informed consent.

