8.2 Objectives of the study

In order to analyze the differences between continuous qualitative variables between the experimental group and the control, the T-Student test will be used for two independent samples, in case the condition of normality can be accepted.

variables in each of the groups. Otherwise, we will proceed with its non-parametric counterpart: U-Mann-Whitney.

In the case of the qualitative variables included in the CRD, the test to be used will be Chi-Square or through Fisher's exact test (when the percentage of expected values less than 5 exceeds 20%).

The possibility of carrying out additional analyzes, depending on the results, with the relevant statistical tests in each case is not ruled out.

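### The only pH outcome named in 7.4 is a success rate below 6.2 that ignores baseline pH; a baseline-adjusted comparison of mean home pH would use data already collected and is likely to be more precise

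*Protocol*

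**What the plan says.** Protocol 7.4 (End points) contains one outcome that measures urinary pH: "Success rate in pH control below 6.2 during the study". The only other item there that mentions pH is the researcher's satisfaction. The unit of the rate (patients, days or readings) is not given.

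Section 6.4 supplies the threshold. The supplement is meant to "maintain the urinary pH at the levels considered as preventive for stent calcification (pH <6.2").

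On entry, 6.2.1 asks only that patients "are recommended to control the pH to avoid scaling / calcification". Section 6.2.2 excludes uric and cystinuric patients who need a different pH control. Neither section sets a pH value.

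Section 7.1 lists, among the main variables, "Urinary pH level and control of it below 6.2 (urine 2h fasting and home self-control with Lit-control®pH Meter"). Section 7.2 describes the fasting sample as "Urine analysis of 2 hours in basal fasting". It is requested at V0 (6.3.3) and not mentioned for the final visit (6.3.4), so on-treatment pH comes from the once-daily first-morning home readings.

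For continuous variables, 8.2 says "the T-Student test will be used for two independent samples", with Mann-Whitney U if normality fails. No covariate is mentioned.

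Section 2 fixes the regimen at 1500 mg/day of L-methionine and cites three pH results. One, at 1500 mg, is described as "resulting in a pH level for 24h between 5.98 and 6.3216"; the last two digits are a reference number, so the range is 5.98 to 6.32. A single 1500 mg dose gave 6.0 in a second source. A third reports a fall from 7.5 to 5.5 at 1500–3000 mg/day.

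**The concern.** A rate below a fixed cut records only the side of 6.2 on which a patient ends. Someone who starts and stays at 5.6 on placebo is a success, although nothing has changed. Someone who falls from 7.5 to 6.3 on the supplement is a failure, although the pH has moved by more than a unit. With no entry limit on pH, the first kind of patient can be enrolled. One of the three cited results lies on both sides of the cut, so the second kind can occur too.

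This outcome serves the secondary objective on pH control. It is also the mechanistic link to the primary incrustation score. If it is insensitive, a real acidifying effect could look weak on the one pH line that 7.4 names. The baseline fasting pH that would sharpen the comparison is collected, but 8.2 makes no use of it.

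**Working it through.** **The plan's own figure.** The sample size in 6.8 concerns the incrustation score, not pH, but it fixes the arm size used here. A two-sample t-test with effect size 0.6, power 80% and two-sided alpha 0.05 (alpha is not stated, so assumed) needs 44.59 per arm. Multiplying by π/3 for Mann-Whitney gives 46.69, so 47 per arm and 94 in total. Then 94/0.9 = 104.4, so 105. Both stated figures reproduce.

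**Inputs for pH.** The protocol gives the cut (6.2), 1:1 allocation and, from 6.8, 47 per arm. It gives no pH mean, between-patient SD or expected shift, so these are assumed. Patient mean home pH is taken as normal and the rate as one yes/no result per patient.

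**Formulas.**
- Placebo success: p0 = Φ((6.2 − μ)/SD). Treated success: p1 = Φ((6.2 − μ + shift)/SD).
- Rate: pooled two-proportion z-test, two-sided 0.05, power by exact binomial enumeration.
- Mean pH: two-sample t-test with d = shift/SD.
- Baseline-adjusted mean pH: the same with SD × √(1 − r²).

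**One case by hand** (μ = 6.2, SD = 0.5, shift = 0.3). p0 = Φ(0) = 0.500 and p1 = Φ(0.6) = 0.726, with mean 0.613. The null SE is √(2 × 0.613 × 0.387/47) = 0.1005. The alternative SE is √((0.250 + 0.199)/47) = 0.0977. Power ≈ Φ((0.226 − 1.96 × 0.1005)/0.0977) = Φ(0.30) ≈ 0.62; exact enumeration gives 0.61. For mean pH, d = 0.3/0.5 = 0.6 and power is 0.82. With r = 0.5 the SD becomes 0.5 × 0.866 = 0.433 and power is 0.91.

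**Shift 0.3, 47 per arm:**

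| Placebo mean | SD | Placebo success | Treated success | Power, rate | Power, mean pH | Adjusted, r = 0.5 |
|---|---|---|---|---|---|---|
| 5.8 | 0.5 | 79% | 92% | 46% | 82% | 91% |
| 6.0 | 0.5 | 66% | 84% | 55% | 82% | 91% |
| 6.2 | 0.5 | 50% | 73% | 61% | 82% | 91% |
| 6.4 | 0.5 | 34% | 58% | 63% | 82% | 91% |
| 5.8 | 0.6 | 75% | 88% | 38% | 67% | 79% |
| 6.0 | 0.6 | 63% | 80% | 44% | 67% | 79% |
| 6.2 | 0.6 | 50% | 69% | 47% | 67% | 79% |
| 6.4 | 0.6 | 37% | 57% | 48% | 67% | 79% |

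**Sensitivity.**
- *Higher baseline.* At placebo mean 7.0, placebo success is only 2–9% (SD 0.4 to 0.6). Power for the rate is still low, 35–42% against 67–95% for mean pH, because few patients in either arm cross the cut.
- *Larger shift.* With shift 0.5 and SD 0.6, the rate has 82–89% power at placebo means 6.0 to 6.5, against 98% for mean pH. With SD 0.4 and means 6.2 to 6.5, both exceed 99%.
- *Weaker correlation.* With shift 0.3 and r = 0.2, adjusted power is 84% (SD 0.5) or 69% (SD 0.6), little above the unadjusted 82% and 67%.

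**The cited 5.98 to 6.32.** If treated patients averaged 5.98, 23–36% of them would lie at or above 6.2 (SD 0.3 to 0.6). If they averaged 6.32, 58–66% would. This is indicative only: the cited range is a 24-hour result, whereas the home readings are first-morning urine.

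**The case against.** The strongest reply is that pH level is already in the plan. Section 7.1 lists it among the main variables and 8.2 provides a continuous test. Nor is 7.4 a complete list, since it does not name the 0–3 incrustation score on which the trial is sized. This stands: absence from 7.4 does not show that pH level will go uncompared. It does not answer the lack of baseline adjustment in 8.2, or the choice of the rate as the one pH outcome that 7.4 names.

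The per-patient yes/no is inferred. If the rate were each patient's share of readings below 6.2, less information would be lost and the power figures above would not apply. An analysis plan that is not shown may define the unit or add covariates, and 8.2 leaves room for further analyses.

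Four stronger readings are tempting, and the protocol does not support them.
- *Misclassification.* Under the target in 6.4, a patient at 5.6 is controlled and one at 6.3 is not. The rate is a legitimate measure of target attainment.
- *Bias.* Randomisation should spread patients with low baseline pH over both arms. The cost is precision.
- *The expected response straddles the cut.* Only one of three cited results does; the others, 6.0 and 5.5, lie below it.
- *Contradictory targets.* Section 2 reports from a guideline that "urinary acidification with L-methionine up to pH 5.8 - 6.2 is recommended" as a therapeutic measure for certain calcifications. Section 6.4 states this trial's preventive level. The two differ in purpose and do not clearly conflict.

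**Conclusion.** The point holds as one of precision on a secondary outcome. The pH end point named in 7.4 takes no account of baseline, enrolment is open to patients at any pH, and 8.2 plans only unadjusted tests although baseline fasting pH is recorded. If the rate is scored once per patient, the contrast is diluted and power is lost.

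The size cannot be fixed from the protocol. The illustration of about 38–63% power for the rate, 67–82% for mean pH and 79–91% after adjustment rests entirely on assumed values: shift 0.3, SD 0.5 to 0.6, placebo mean 5.8 to 6.4 and r = 0.5. The loss is small if the shift is larger and the baseline mid-range. If baseline pH is well above 6.2, the loss can be large, but not because untreated patients succeed. The primary comparison is not affected.

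**What to change.** In 7.4 and 8.2, name as the main pH comparison the between-arm difference in each patient's mean home-meter pH over follow-up, estimated by ANCOVA with the baseline 2 h fasting pH as covariate. Keep the success rate below 6.2 as a supportive measure of target attainment. State whether it is taken over patients, days or readings, and report it separately for baseline pH below 6.2 and for 6.2 or above.

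The cost is a few lines of wording and slightly more analysis, with no new data, visit or patient. The gain from adjustment depends on how well fasting pH at V0 correlates with first-morning home pH. That correlation is unknown, and it may be weak where the V0 sample precedes stent placement.
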